3.5 Trial participants

3.5.1 Healthcare providers

Training participants will be the HCPs from target HCFs. To respect routine service delivery in the participating HCF, training in ANC and PNC will be provided to ideally 80% of the HCPs providing ANC and PNC within the appropriate step. Only the HCP trained within the steps will be observed as part of the trial. Other HCP will be trained as part of the implementation program but will not be observed.

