3.2.2 Clusters

Delivery of essential components will be assessed through the observation of ANC-PNC visits by external data collectors. At each healthcare facility at least two HCPs (three for bigger facilities) will be observed in four of the eight assessment periods. For each HCP four HCP-

client interactions (ANC or PNC visits) would be observed in at least three of the four assessment periods for their HCF.

The design to be deployed is a cluster randomised design since the HCPs for whom data are to be collected are clustered, by HCF. For the assessment of delivery of essential components by an individual HCP at a single HCF in each step, a second level of clustering arises: the data obtained from observation of up to 4 different ANC-PNC visits also forms a cluster as described in **Figure 1**.

Figure 1: Schematic representation of sequences available to randomise to HCFs

	Assessment period							
Group	1	2	3	4	5	6	7	8
Α	0	Т	0		0		0	
В		0	T	0		0		0
С	0		0	Т	0		0	
D		0		0	Т	0		0
E	0		0		0	Т	0	
F		0		0		0	Т	0

O = Observation

T = Training

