3.3 Randomisation and assessment periods

Each HCF will be randomised to a Group (A, B, C, D, E, F) which determines the assessment periods (2 to 7) in which the ANC-PNC training workshop will take place. All randomisations will be done using the runiform() function in Stata.

Each Group will then be assessed in alternating assessment periods, timed so that assessment does not occur in a period in which training is delivered, since this is a 'transition' month for which data would not be useful for analysis. For those randomised to Groups A, C and E observation of ANC-PNC visits will commence at the beginning of the trial (assessment period 1). For those randomised to Groups B, D and F, it will commence after one and a half months (assessment period 2). All healthcare staff providing ANC and/or PNC in participating HCFs will attend the 'skills and drills' training workshop to ensure they have the knowledge and skills to provide integrated ANC and PNC (including able to provide each essential component as set out in **Appendix 1**).

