The consenting process for the healthcare facility manager will cover all elements of the trial, including details and organisation of the intervention and the required inputs concerning the conduct of the trial and data collection processes. Once explained, opportunities to familiarise with the trial information, ask questions and seek further clarifications as needed will be encouraged. In-country and LSTM staff will be on stand-by to address any queries and provide details as needed. The facility in-charge (or another relevant member of the leadership team) will be asked to provide consent on behalf of the healthcare facility. The data collection processes and details will be explained and discussed in detail as part of visits conducted to each of the HCF by the study team. The stepped-wedge calendar will be explained to them and at least 1 week before the beginning of each step, the study team will contact the facility that will have ANC-PNC observed to plan for the data collector's visit. No observation will be conducted unexpectedly, and data collectors will work based on the staff roster to ensure the participating healthcare providers are observed.

The confidentiality and privacy of the observed facility staff, as well as patients will be stressed. It will also be explained that the data collection, while centring around care provided, will not collect any non-anonymised details from patients. All involved will receive all information detailing the purpose of the assessment, what is involved, and that the research team will be available to answer any questions.

Consent from healthcare providers will be sought before the launch of the trial, then refreshed before conducting each day of observation, and consent from clients before asking for inputs each visit observed. Each day of observation, the information about the study will be shared with each participating healthcare provider.

Clients will be women who receive antenatal or postnatal care either/both for themselves or/and their baby. The purpose of the data collection will be explained by the data collector both to the HCP and the client, including the type of information that will be collected, as well

as the voluntary nature of their participation. It will be reiterated that participant confidentiality and anonymity will be upheld.

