3.8 Statistical analysis

Period is defined as the assessment period of the trial which observation occurred, or for which measurement took place. Data will be omitted from analysis when values are missing for either the outcome or a covariate required for the analysis of that data value. Missing data will not be replaced.

For each ANC/PNC visit observed the proportion of essential components addressed will be calculated (ECall). Data analysis will be performed using Stata version 14.2 or later. To derive an estimate of the benefit of providing ANC-PNC training, linear regression within a generalised linear mixed model (GLMM) framework will be used to analyse the primary outcome data (ECall). GLMMs are appropriate in the context of stepped wedge trial designs as they allow for clustering and address confounding of intervention effects and time (Hemming et al 2015). The analysis will include a binary intervention factor which indicates if the data were collected pre- or post- ANC-PNC training and fixed effects for study month to account for any underlying secular trend. Random effects will be included for HCF (cluster), HCP within HCF and HCF by month interaction. The effects of the intervention will be reported as an adjusted (for month, HCF and HCF by month clustering) odds ratios (OR), with 95% confidence intervals.

Reporting will follow CONSORT guidelines for reporting stepped wedge trials current at the time of publication of the results (currently Hemming et al, 2018), Available data will be analysed using an intention to treat approach and also as implemented, if there are any protocol deviations, to assess the sensitivity of results to the analysis approach adopted.

The baseline delivery of essential components has been assumed to be around 50% as the precision of estimates is poorest for this value. If the level is below 50% there will be greater potential for improvement and greater power to detect an improvement of a specified magnitude. However, if the level is close to 100% it will not be possible for a statistically significant benefit of the intervention to be demonstrated. In such circumstances administrative analyses will be conducted.

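### Restricting observation to HCPs trained within their step makes cohort membership depend on an event after randomisation, which conflicts with the intention-to-treat analysis

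*Protocol*

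**What the plan says.** Section 3.3 randomises each facility (HCF) to one of six groups, which sets its training in one of assessment periods 2 to 7. The same section says of the workshop: "All healthcare staff providing ANC and/or PNC in participating HCFs will attend".

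Section 3.5.1 differs. There, "training in ANC and PNC will be provided to ideally 80% of the HCPs providing ANC and PNC within the appropriate step". It continues: "Only the HCP trained within the steps will be observed as part of the trial". Of the remaining staff it says: "Other HCP will be trained as part of the implementation program but will not be observed".

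Under section 3.2.2, at least two HCPs per facility (three in bigger facilities) "will be observed in four of the eight assessment periods". Section 3.5.3 adds: "Consent from healthcare providers will be sought before the launch of the trial".

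For the analysis, section 3.8 says: "Available data will be analysed using an intention to treat approach and also as implemented", the latter if there are protocol deviations. The model carries a pre- or post-training indicator and random effects for HCF, HCP within HCF and HCF by month.

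**The concern.** The trial follows a cohort of HCPs from the control state into the intervention state. Control observations come first, yet section 3.5.1 ties observation to having been trained in the step. Whether an HCP attends is settled after randomisation and may be related to workload, motivation or competence. Selecting on it gives up, at HCP level, the protection that intention to treat is meant to provide.

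The HCP most affected is one who is enrolled, remains in post and misses the workshop. Her later visits could be observed at no extra cost and belong in an analysis by allocated step, but the sentence excludes them. The protocol foresees instability of this kind: section 3.7 names retention of healthcare providers as something the pandemic could affect, and Appendix 3 counts how many trained staff still provide ANC and PNC.

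**Working it through.** **Inputs.** Observation and training periods are from Figure 1. The 18 HCFs, 2 to 3 HCPs per HCF, 4 visits per HCP and four assessed periods are from Box 2. Periods last 1.5 months (Table 3). Equal allocation, 18/6 = 3 HCFs per group, is assumed.

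**1. When could the rule be applied?**

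| Group | Trained in period | Observed before | Observed after |
|---|---|---|---|
| A | 2 | 1 | 3, 5, 7 |
| B | 3 | 2 | 4, 6, 8 |
| C | 4 | 1, 3 | 5, 7 |
| D | 5 | 2, 4 | 6, 8 |
| E | 6 | 1, 3, 5 | 7 |
| F | 7 | 2, 4, 6 | 8 |

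Scheduled facility-periods: 18 × 4 = 72. Before training: 3 × (1 + 1 + 2 + 2 + 3 + 3) = 36, or half. None of these can be restricted to trained HCPs when the data are collected. In Group F the first observation is in period 2 and training in period 7, which is 5 × 1.5 = 7.5 months later.

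**2. What happens to an enrolled HCP?**

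- She attends on schedule: the sentence has no effect.
- She leaves: there are no further outcomes under any wording. This is attrition.
- She stays but misses the workshop: the sentence can be followed only by stopping observation or by also dropping her earlier data. Stopping leaves her in the control data but not in the intervention data; dropping removes her altogether. Either way her post-training-period outcomes are lost: three periods in Groups A and B, two in C and D, one in E and F.

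Sections 3.5 and 3.6 do not say that an HCP in the third position is kept.

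**3. Does keeping her add fieldwork?** The client totals in section 3.5.3 reproduce as 18 × 2 × 4 × 4 = 576 and 18 × 3 × 4 × 4 = 864 (HCFs × HCPs × visits × periods). They already count every observed HCP in all four periods, so following the same HCPs regardless of attendance adds no visits to the plan.

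**4. What might the fix cost in effect size?** The protocol's own figure comes first. SD = √(0.01 + 3 × 0.0225) = 0.278, and 0.81 × 0.278 = 0.225; with the SD rounded to 0.28, section 3.6 gives 0.23 at 80% power. Assume a two-sided 5% level, consistent with the 95% intervals in section 3.8. The implied standard error is 0.225/(1.960 + 0.842) = 0.080. If a fraction c of the observed HCPs attend and the others gain nothing, the average effect is 0.225c and power is Φ(0.225c/SE − 1.960):

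| c (assumed) | Average effect | Power |
|---|---|---|
| 1.0 | 0.225 | 80% |
| 0.9 | 0.203 | 71% |
| 0.8 | 0.180 | 61% |
| 0.7 | 0.158 | 50% |

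These values of c are assumptions about the 2 to 3 observed HCPs. The protocol gives no such rate, and the 80% in section 3.5.1 is not one. The no-gain assumption is also unfavourable, because HCPs not trained in the step are to be trained through the wider programme.

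**The case against.** The strongest reply is that the sentence means HCPs scheduled for the trial's training. Consent precedes launch (section 3.5.3), Table 3 describes a cohort and Table 4 a closed cohort, and section 3.6 expects both HCPs at a two-HCP facility to accept observation in all four periods. This may well be the intent. But the sentence says trained, its companion says the others are not observed, and none of those sections keeps an enrolled HCP who misses the session. If the intent is different, the wording has to change.

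A reader might infer four stronger things that the protocol does not support.

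- *That intention to treat is impossible.* Facilities are the randomised units, and data from observed HCPs can still be analysed by allocated sequence. The gap concerns HCPs who miss training.
- *That the intention-to-treat and as-implemented analyses coincide.* Section 3.6 foresees postponed training. A facility trained late is classified differently by allocated step and by actual date.
- *That the effect is inflated by 1/0.8 = 1.25.* The 80% is planned coverage of all ANC and PNC staff, not attendance among the observed HCPs.
- *That later groups are more strongly selected.* No turnover rate is given. Sections 3.2.2 and 3.7 also want each HCP observed in at least three of four periods, so a Group A HCP must be observed in period 5 or later.

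Two further points stand in part. The HCP random effect reduces confounding by stable differences between HCPs, but it does not supply the missing outcomes. An effect among trained HCPs also fits the objective in section 2.3.1, but section 3.8 promises more than that.

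**Conclusion.** The concern holds in a limited form. As written, section 3.5.1 makes observation depend on a post-randomisation event and cannot be applied prospectively to the half of scheduled facility-periods that precede training (assuming equal groups). It also withholds intention-to-treat outcomes for HCPs who remain in post but miss their session, so the HCP-level estimate moves towards a per-protocol effect among on-schedule attenders. The extent depends on how many of the observed HCPs miss training and how they differ from attenders. The protocol gives neither, so the size and direction of bias cannot be stated. No figure in the protocol is shown to be wrong.

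Sections 3.3 and 3.5.1 also disagree on coverage. If all staff attend within the step, the restriction excludes nobody; if about 80% do, roughly one in five staff falls outside the observable pool. The two can be reconciled if the remainder are trained later through the programme, but section 3.3 does not say so.

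**What to change.** Replace the sentence in section 3.5.1 so that:

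- the 2 to 3 observed HCPs per HCF are named before group allocation is disclosed;
- they are observed in every scheduled period while in post, whether or not they attended training;
- those who leave are reported as attrition.

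In section 3.8, define intention-to-treat exposure by the HCF's allocated step and use actual attendance only for the as-implemented analysis. Reconcile the coverage statements in sections 3.3 and 3.5.1.

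The cost is protocol wording, with no additional HCPs or planned visits. If some observed HCPs miss training, the estimated effect may be somewhat smaller, as the conditional table illustrates.

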3.5.2 Women who have received ANC or PNC

To assess the delivery of essential components during ANC-PNC visits, the observation will happen at the time women receive ANC or PNC at the HCF. Although the care provided by the HCPs is the focus, the clients who are receiving care will be asked to consent to the visit being observed. Observation will not be done for every woman: All eligible visits will be observed, unless consent is declined, until the four visits have been observed for each participating HCP. We anticipate that up to 12 women (up to 4 visits per HCP, with 2 to 3 HCPs observed per HCF) will be observed at each HCF in each step when delivery of care is observed and assessed.

3.5.3 Recruitment and consent seeking, including withdrawal, voluntary participation, confidentiality of data

Informed consent

With healthcare facilities pre-identified for the trial using the inclusion criteria specified in Section 3.1.1, the sensitisation and consent seeking of HCFs and HCPs will be done well in advance of the trial. This will involve sharing relevant study information in writing but also engaging in discussions. The final shape of the trial will be agreed with inputs from the MoH as well as other local partners to ensure its suitability and feasibility. Once healthcare facilities which meet the inclusion criteria are identified, their managers will be contacted to invite them to take part in the trial. All information sheets will be shared with heads of facilities and any identified key-staff prior to the launch of the trial. The purpose and level of effort required from the participating healthcare facilities will be explained ahead of the start of the trial, so the in-charge is able to make an informed decision on committing their healthcare facility to the trial.

The consenting process for the healthcare facility manager will cover all elements of the trial, including details and organisation of the intervention and the required inputs concerning the conduct of the trial and data collection processes. Once explained, opportunities to familiarise with the trial information, ask questions and seek further clarifications as needed will be encouraged. In-country and LSTM staff will be on stand-by to address any queries and provide details as needed. The facility in-charge (or another relevant member of the leadership team) will be asked to provide consent on behalf of the healthcare facility. The data collection processes and details will be explained and discussed in detail as part of visits conducted to each of the HCF by the study team. The stepped-wedge calendar will be explained to them and at least 1 week before the beginning of each step, the study team will contact the facility that will have ANC-PNC observed to plan for the data collector's visit. No observation will be conducted unexpectedly, and data collectors will work based on the staff roster to ensure the participating healthcare providers are observed.

The confidentiality and privacy of the observed facility staff, as well as patients will be stressed. It will also be explained that the data collection, while centring around care provided, will not collect any non-anonymised details from patients. All involved will receive all information detailing the purpose of the assessment, what is involved, and that the research team will be available to answer any questions.

Consent from healthcare providers will be sought before the launch of the trial, then refreshed before conducting each day of observation, and consent from clients before asking for inputs each visit observed. Each day of observation, the information about the study will be shared with each participating healthcare provider.

Clients will be women who receive antenatal or postnatal care either/both for themselves or/and their baby. The purpose of the data collection will be explained by the data collector both to the HCP and the client, including the type of information that will be collected, as well

as the voluntary nature of their participation. It will be reiterated that participant confidentiality and anonymity will be upheld.

All participants will be given the opportunity to ask questions, which will be fully answered. Due to the nature of the observation, time given for decision-making may be limited, but care will be taken to minimise any pressure for considering whether to participate from the women. To allow the women time to consider participating to the study, information will be given at different point of contact in the facility whenever possible, such as during registration or health promotion sessions. They will be allowed as long as they wish to decide and should have all the waiting time to reflect. Due to the usual capacity of healthcare facilities in Chad, ANC-PNC are usually crowded with women waiting a long time, and consultation kept short. All women will be informed that they can take time and decide later to be observed, however, there is a low chance that any would find worth to leave and come another day for the visit, due to the time and resources consumed. For women who may not be able to read and write, consenting will take place with the assistance of an independent witness.

The total number of HCPs to be trained and observed will be up to 54. At each HCF up to 12 women will be observed in each of four assessment periods. Thus, the total number of women asked to consent to be observed will be between 576 and 864.

Information on the availability of equipment and consumables for ANC-PNC components under assessment, will be retrieved from routine data records and directly from HCP. This step will therefore not require obtaining client consent.

Voluntary participation and right to withdraw

The head of the facility, healthcare providers, for observation and retrieval of information from patient-held records, will be informed of the voluntary participation and their right to withdraw without any consequences.

Clients for observation will be informed of the voluntary participation and their right to withdraw at any time during the observation without any consequences. However, it will not be possible to retrieve data once fully anonymised.

Confidentiality and anonymity

All patient data and/or information on individual patient outcomes collected will be recorded anonymously. No aspect of the assessment will involve non-anonymised patient details. Data collectors will observe sensitive confidential information (e.g. results of HIV tests). They will be required to maintain the confidentiality of all such information. In the unlikely event that non-anonymised data are accidentally collected, they will be destroyed and excluded from analysis.

It will not be possible, given the intention of this trial, to anonymise facility data. That is, facility names will be captured. However, the intention of this trial is to facilitate work that will improve the functioning of facilities for improved care, which is within the mandate of these facilities. While the standard reporting and any trial publications will not use facility names in the reporting, if required, for the use of the MoH the facility-level details, however,

will be collated and the final analysed data set will be shared using password protected files to limit the risk of disclosing the details to unintended audiences.

